##### **4.3.6.2. Handling of Missing Result Data**

No imputation will be done of missing result data unless otherwise specified. That is, an observed case (OC) analysis will be performed. Endpoints analyzed via MMRM handle missing data via the maximum-likelihood function.

For MCS [REDACTED] a multiple imputation procedure will be used as described in section 6.2.2.2. [REDACTED]

For analyses of binary endpoints in the secondary efficacy endpoints, the non-responder imputation (NRI) method will be used for missing value imputation in addition to the observed case (OC) analysis.

##### **4.3.6.3. Censoring of Time to Event Data**

Not applicable.

#### **4.3.7. Handling of Values Below or Above a Threshold**

Results of continuous parameters, as well as normal limits of these reported as below (or above) the detection limit will be imputed by the value one precision unit smaller (or larger) than the detection limit itself. In listings, the original value will be presented.

Example: if the database contains the value “<0.04”, then for the descriptive statistics the value “0.03” will be used. The value “>1000” will be imputed by “1001”.

For PK data, values below the limit of quantification will be imputed by 0 for the calculation of descriptive statistics presentation; except for the geometric mean and the geometric CV%, where

it will be imputed as lower limit of quantification (LLOQ)/2. These values will be listed as “below lower limit of quantification (BLOQ)”.

#### **4.3.8. Handling of Outliers**

There will be no exclusion of outliers, all measured values will be included in the analyses.

#### **4.3.9. Stratification Factors**

Not applicable.

### **4.4. Presentation of Results**

#### **4.4.1. Presentation of Treatment Groups**

Results will be presented by treatment group:

- GLPG3970 400 mg q.d.
- Placebo

In the Subject Information, a grand total “All Subjects” will be added to summarize all subjects over all treatment groups in tables.

#### **4.4.2. Calculation of Descriptive Statistics**

For continuous parameters, descriptive statistics will be presented when  $N \geq 2$ . When  $N = 1$ , the observation will not be shown in tables nor in figures of summary statistics but will only be listed.

Descriptive statistics will include:

- the number of non-missing data points (n);
- the arithmetic mean;
- the standard error (SE) and standard deviation (SD);
- the median, minimum and maximum;
- 90% confidence interval (CI) of the mean (if indicated in the relevant section).
- [REDACTED]

For PK data, descriptive statistics will include:

- the number of non-missing observations (n);
- the number of data points above the LLOQ;
- the arithmetic mean;
- SE and SD;
- the median, minimum and maximum;
- the coefficient of variation (CV%);
- the geometric mean and geometric CV%.

If less than 50% of the subjects have quantifiable values, only the number of subjects with data, number of data points above the LLOQ, the arithmetic mean, median, minimum, and maximum will be presented with the original calculated value. The other descriptive statistics will be listed as “NC” (not calculated).

If the calculated descriptive statistic is BLOQ, then it will be presented as “BLOQ”.

Individual values and descriptive statistics of concentrations and PK parameters will be presented with 3 significant digits.

#### **4.4.3. Calculation of Percentages**

Frequencies and percentages will be generated for categorical parameters.

For event-type data (e.g. AEs), the denominator will be all subjects in the analysis set and analysis period. For other data (e.g. worst-case analysis of assessments), the denominator will be

all subjects with (post-baseline) data for the parameter, in the analysis set and analysis window/period.

## 5. INTERIM ANALYSES AND INTERNAL DATA SAFETY MONITORING COMMITTEE

No formal interim analysis is planned for this clinical study.

An internal SMC independent from the study will review unblinded safety data during the course of the study. This Committee may involve external medical experts (such as an expert in the field of UC and an infectious diseases expert) to support data interpretation. The Committee will review unblinded safety data and assess any potential safety issues arising during the conduct of the clinical study, including (but not limited to) any potential issues in the context of the SARS-CoV-2 pandemic. The clinical study team will remain blinded to the allocation of subjects to treatments during the course of the study. The process is described in a separate SMC Charter.

## 6. STATISTICAL ANALYSES

### 6.1. Subject Information

Subject information will be tabulated using the Safety Analysis Set, unless specified otherwise. No inferential testing will be performed, nor will p-values be provided.

Subject information will be tabulated with descriptive statistics per planned treatment group, as well as overall.

#### 6.1.1. Demographic and Baseline Disease Characteristics

The following parameters will be summarized:

- date of ICF signature (listed);
- sex;
- age at signing the ICF (years);
- age, categorized (years):  $18 \leq \text{age} < 65$ ;  $65 \leq \text{age} < 85$ ;  $\text{age} \geq 85$ ;
- race and ethnicity;
- height at baseline (cm);
- weight at baseline (kg);
- body mass index (BMI) at baseline ( $\text{kg}/\text{m}^2$ ) = 
$$\frac{\text{weight} \ (\text{kg})}{\text{height}^2 \ (\text{m}^2)}$$
(BMI will not be recalculated if already available in the database);
- smoking status (Non-smoker/Ex-smoker/Current smoker);
- number pack-years;
- duration of UC (years)  
$$= \frac{(\text{date of first study drug administration}) - (\text{date of initial diagnosis}) + 1}{365.25}$$

If missing day: use 1st day of the month

If missing both day and month: use 1st of January;

- duration of UC, categorized: <6 months; 6 months  $\leq$  duration < 1 year; 1  $\leq$  duration < 3 years; 3  $\leq$  duration < 5 years; 5  $\leq$  duration < 10 years; duration  $\geq$  10 years;
- MCS at baseline;
- [REDACTED]
- [REDACTED]
- MCS-SF at baseline
- MCS-RB at baseline;
- MCS-ES at baseline;
- PGA at baseline;

Demographic and baseline disease characteristics will be listed.

### 6.1.2. Allocation and Randomization

The number of subjects (and percent) per treatment group and overall will be tabulated per country and site.

The following listings will be provided:

- Listing per subject of the study drug kit numbers, study drug batch numbers dispensed/returned.

- Randomization schemes and codes, with the treatment assigned to each subject. This listing includes a flag in case of discrepancies or errors between the assigned and the actual treatment taken, and should also include flags declaring any (potential) unblinding.

### **6.1.3. Disposition Information**

The following tabulations will be provided, by treatment group and overall:

- The number of subjects screened, not-randomized (including reasons), randomized (treated and not treated), and treated with GLPG3970 and Placebo.
- Number (percent) of subjects randomized per country and site.
- The number (percent) of subjects in each analysis set as defined in [Section 4.1](#).
- The number (percent) of subjects per analysis window as defined in [Section 4.3.3](#).
- The number (percent) of subjects who completed/discontinued the study drug administration schedule and the reasons for discontinuation.
- The number (percent) of subjects who completed/discontinued the study and the reasons for discontinuation.

Additionally, the following information will be provided in listings:

- Subject identification and randomization (country, site number, investigator, subject number).
- Randomization number and date, planned and actual randomization group, with flags for any discrepancies.
- Subjects excluded from the safety and full analysis sets, including reasons.

### **6.1.4. Protocol Deviations and Eligibility**

Major protocol deviations are determined and recorded while the study is ongoing, and the list is finalized prior to database lock (and unblinding). For more details, please refer to the Protocol Deviations Plan.

The number (percent) of subjects with major protocol deviations will be tabulated, overall and per class of deviation, by treatment group and overall.

All available information concerning major protocol deviations, including COVID-19 related verbatim, violations on eligibility criteria and subjects not treated will be listed. Protocol deviations leading to the exclusion of subjects from any analysis set, as applicable, will be flagged.

COVID-19 related protocol deviations will be listed together with the rest of major protocol violations. The fact that they are COVID-19 related will be present in that listing.

### **6.1.5. Medical History and Concomitant Diseases**

Frequency tabulations, per treatment group and overall, per system organ class and preferred term will be provided for the medical history findings (i.e., conditions no longer present at the start of the study) as well as for the concomitant diseases (i.e. conditions present at the start of the study) using Medical Dictionary for Regulatory Activities (MedDRA) coding dictionary.

All medical history findings and concurrent diseases will be listed separately.

### **6.1.6. Ulcerative Colitis History**

Frequency tabulations, per treatment group and overall, per system organ class and preferred term will be provided for the UC disease history.

In addition, frequency tabulations, per treatment group and overall, will be provided for the following parameters.

- extent of disease at time of most extensive disease activity per Montreal Classification;
- previous treatment failure and corresponding treatments;
- colonoscopy history (yes/no);
- stool history (number of stools per day under normal (healthy/remission) conditions)

All UC history will be listed.

### **6.1.7. Prior and Concomitant Medications**

#### **6.1.7.1. Coding of Reported Terms**

All prior and concomitant medication terms will be coded in the database using the World Health Organization (WHO) drug coding dictionary version.

#### **6.1.7.2. Classification of Medications**

All prior and concomitant medication records will be categorized as follows, considering their date and flags indicating the relative timing versus study (drug) start or end (before, after, ongoing):

- Prior only: when the record ended before the first study drug administration date.
- Concomitant only: when the record started on or after the first study drug administration date.
- Prior and concomitant: when the record started before the date of first study drug administration, and ended on or after this point, or continued.

When the start or end date of the prior and concomitant medication records are incomplete (and no flags indicating relative timing are available), the date of first study drug administration will

be considered to the same level of information provided by these incomplete dates to categorize the timing of these records. This means that a record only having month and year will be categorized comparing only to the month and the year of the date of first study drug administration.

#### 6.1.7.3. Calculation of Relative Days

For both the start and the end dates of the concomitant medication records, their day relative to the day of first study drug administration will be calculated as described in [Section 4.3.1](#).

#### 6.1.7.4. Presentation of Results

A frequency tabulation per planned treatment group and overall of the Anatomical Therapeutic Chemical (ATC) classification classes level 4 by therapeutic subgroup (ATC level 2) and generic term of the prior medication (defined as 'prior only' and 'prior and concomitant') will be provided as well as of the concomitant medication (defined as 'concomitant only' and 'prior and concomitant').

A listings of prior and concomitant medications will be provided. Also, prior and concomitant corticosteroid listing will be provided separately (the list of the ATC codes to be selected in this listing will be provided by the Galapagos medical services).

#### 6.1.8. Procedures

Procedures results will only be listed.

#### 6.1.9. Exposure to Study Drug and Compliance

##### 6.1.9.1. Derivation Rules

###### Derived Parameters: Extent of Exposure to Study Drug

- *Total treatment duration* (days) = last study drug administration date – first study drug administration date + 1 day.
- *Total treatment duration, excluding days off study drug*: Sum of the number of days with any study drug administration.
- *Total treatment duration, full compliance* (days): Number of days where the complete volume of IP has been administered.

###### Derived Parameters: Compliance

- Overall compliance (%) =  $100 \times \frac{\text{number of doses actually taken}}{\text{number of doses that should have been taken}}$
- Percent days with any intake (%) =  $100 \times \frac{\text{total treatment duration,excluding days off drug}}{\text{total treatment duration}}$
- Percent days full compliance (%) =  $100 \times \frac{\text{total treatment duration,fully compliant}}{\text{total treatment duration}}$

### **6.1.9.2. Presentation of Results**

Summary statistics per planned treatment group and overall will be provided for each compliance and extent of exposure parameter for study drug administration. Frequency tables will be provided for the compliance parameters, using the following categories:  $<80\%$ ;  $80\% \leq x < 100\%$ ;  $100\%$ ;  $100\% < x \leq 120\%$ ;  $> 120\%$ .

All original study drug administration records will be listed per subject. The listing will include all deviations from study drug schedules such as missed or reduced doses and GLPG3970/placebo switches and will also include food intake status at the time of study drug administration.

Study drug exposure and compliance data will be listed.

## 6.2. Efficacy Analyses

Efficacy analyses will be performed on the FAS.

Tabulations will be shown per planned treatment group.

### 6.2.1. Level of Significance

Statistical tests for efficacy analysis will be done at a 2-sided significance level of 10%.

### 6.2.2. Primary Efficacy Parameter

The primary endpoint for this study is the change from baseline in total MCS at Week 6. The total MCS score will be calculated only at baseline and week 6.

The MCS ranges from 0 to 12. A lower score means a better subject condition. It consists of 4 subscores. Each sub-score ranges from 0 to 3. The four components of the MCS are (see [Appendix III](#)):

- MCS-SF subscore
- MCS-RB subscore
- MCS-ES subscore
- PGA

For calculation of the MCS subscores performed by the investigator, MCS-RB and MCS-SF, subjects will be instructed to record symptoms of RB and SF daily in a diary.

The information on the UC symptomatology of the last 3 consecutive available days in the diary collected from the last week, will be used to score the MCS-RB and MCS-SF subscores, excluding the day before the endoscopy (with bowel preparation), the day of the endoscopy and the day after the endoscopy.

The PGA will be scored by the investigator or trained sub-investigator at visits specified in the Schedule of Activities.

#### 6.2.2.1. Derivation Rules

The MCS will be calculated based on the following formula:

$$\text{MCS} = \text{MCS-SF} + \text{MCS-RB} + \text{MCS-ES} + \text{PGA}$$

If one of the component is missing at a specific analysis window, total score will not be calculated for that analysis visit and will be set to missing.

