8.4. Efficacy Assessments

8.4.1. Endoscopy

An endoscopy (either a surveillance colonoscopy or flexible sigmoidoscopy, see below) will be performed on the visits specified in the Schedule of Activities in Section 8.11 (see also Section 8.1, “[Timing of Assessments](#)”).

At screening visit 2:

- a. In subjects with a history of UC ≥ 8 years:
 - i) With a colonoscopy performed more than 24 months prior to screening, a surveillance colonoscopy will be performed.
 - ii) With a colonoscopy performed less than 24 months prior to screening, a flexible sigmoidoscopy will be performed.
- b. In subjects with a history of UC < 8 years:
 - i) A flexible sigmoidoscopy will be performed, irrespective of the time of the last colonoscopy.

At Visit 5 (or at the ED visit, if applicable):

- a. A flexible sigmoidoscopy will be performed for all subjects in the study.

Videos of the flexible sigmoidoscopy or of the screening surveillance colonoscopy, will be recorded. These will be reviewed and scored by blinded central reviewer(s) using the MCS-ES and [REDACTED] indices (refer to [Appendix 10](#) and [Appendix 11](#)). The MCS-ES (Schroeder,

Tremaine, & Ilstrup, 1987) [REDACTED] screening scores will be reported to the clinical site.

Details of the endoscopy, including bowel preparation before endoscopy, as well as the collection and processing of video films will be provided in a separate imaging charter.

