Appendix 10: Mayo Scoring System

A. Mayo Scoring System

| | 0 | 1 | 2 | 3 |
|--|----------------------------|--|---|---|
| Stool frequency [MCS-SF] ^a | Normal | 1 -2 stools above normal | 3 -4 stools above normal | >4 stools above normal |
| Rectal bleeding [MCS-RB] ^a | No blood seen | Streaks of blood less than half the time | Obvious blood with stool most of the time | Blood alone passed |
| Flexible sigmoidoscopy [MCS-ES] ^b | Normal or inactive disease | Mild disease (Erythema, decreased vascular pattern, no friability) | Moderate disease (Marked erythema, absent vascular pattern, friability, erosions) | Severe disease (Spontaneous bleeding, ulceration) |
| Physician's global assessment [PGA] ^a | Normal | Mild disease | Moderate disease | Severe disease |

a (Lewis J. , et al., 2008)

b (Schroeder, Tremaine, & Ilstrup, 1987)

The total MCS equals the sum of all 4 subscores.

The [REDACTED] equals the sum of the MCS-SF, MCS-RB and PGA subscores.

The [REDACTED] (FDA CDER, 2016) equals the sum of the MCS-SF, MCS-RB and MCS-ES subscores.

| | | | |
|------------|------------|------------|------------|
| | [REDACTED] | [REDACTED] | [REDACTED] |
| [REDACTED] | [REDACTED] | [REDACTED] | [REDACTED] |
| [REDACTED] | [REDACTED] | [REDACTED] | [REDACTED] |
| [REDACTED] | [REDACTED] | [REDACTED] | [REDACTED] |
| [REDACTED] | [REDACTED] | [REDACTED] | [REDACTED] |

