**Table 3: Analysis visit window for non-PK data**

Visit date and time	Relative day (ADY)	Assessment visit (VISIT)	Time window (in ADY)*	Target day	Analysis visit (AVISIT)
On or before first study drug administration	$\leq 1$	Last assessment at any point in time before first study drug administration	$\leq 1$	1	Baseline
After first study drug administration	>1	Any scheduled (non follow-up), unscheduled, or early discontinuation visit	2 to 12	8	Week 1
			13 to 22	15	Week 2
			23 to 36	29	Week 4
			37 to 49*	43	Week 6
		Follow-up	CRF collected follow-up visit		Follow-up

\*For Week 1, Week 2, Week 3, Week 4, Week 5 and Week 6, time windows will be applied excluding assessments performed more than 2 days after the last dose of IP. Except for Endoscopy and [REDACTED] where assessments performed more than 7 days after last dose will be excluded and the Week 6 analysis window will be 37 to 52 days.

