### 6.2.2.2. Analyses Methods

The MCS data will be analyzed descriptively as actual (observed) values and changes from baseline.

An ANCOVA will be used on the MCS change from baseline to compare treatment groups, with treatment as a fixed effect and the baseline MCS as a continuous covariate. Missing data will be imputed using Rubin's multiple imputation (Rubin, 1987). A multivariate normal model will be used as the imputation model. The Markov chain Monte Carlo (MCMC) method will be used to sample from the posterior distribution of the model parameters. The following variables will be used to impute missing data at week 6: MCS baseline value and [REDACTED] at baseline, week 2, 4 and week 6. The imputation model will be separately fitted for each treatment arm. In case the covariance matrix is singular, the imputation method will be changed as follows. The following variables will be used to impute missing data at week 6: MCS baseline value and [REDACTED] at baseline, week 2, 4 and week 6 and treatment arm. The imputation model will no longer be fitted separate for each treatment arm. If the imputation is still problematic after that, then treatment will not be used as a variable for imputation and imputation will not be done separately per treatment arm.

For each imputed dataset, the above ANCOVA model will be used to derive the least squares estimate and standard error of the treatment difference in mean change, and the LS means and standard error for the mean change within each treatment group. Then, these results will be combined using Rubin's rules (Rubin, 1987) to obtain the global least squares estimate and standard error of the treatment difference in mean change, its associated two-sided 90% confidence intervals and p-values for treatment group comparison. The global LS means and standard error and their associate two-sided 90% CIs for the mean change within each treatment group will be also obtained. Further details are provided in Appendix VIII with the SAS code.

The number of patients in the analysis population and number of patients in the analysis will be provided by treatment group.

Listings will be provided for MCS.

#### Sensitivity Analysis 1

As a sensitivity, the above analysis will be performed only allowing data points taken no more than 2 days after day of last dose.

#### Sensitivity Analysis 2

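### If a Week 6 stool, bleeding or PGA subscore is missing, the SAP appears to impute the total Mayo score without using the endoscopy subscore that was measured

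*SAP*

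**What the plan says.** **Scoring.** SAP 6.2.2.1 defines MCS as SF + RB + ES + PGA and adds: "If one of the component is missing at a specific analysis window, total score will not be calculated for that analysis visit". SAP 6.2.2 states: "The total MCS score will be calculated only at baseline and week 6".

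**Imputation.** SAP 6.2.2.2 reads "The following variables will be used to impute missing data at week 6: MCS baseline value and", followed by a blacked-out score at baseline and Weeks 2, 4 and 6. The planned model is by arm: "The imputation model will be separately fitted for each treatment arm". If the covariance matrix is singular, the SAP moves to a pooled model with treatment as a variable, and then to a pooled model without treatment.

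**Endoscopy.** Protocol 8.4.1 schedules it at screening visit 2 and at Visit 5 or the ED visit, where "A flexible sigmoidoscopy will be performed for all subjects in the study". No MCS-ES exists at Weeks 2 or 4.

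**A score that needs no endoscopy.** Protocol Appendix 10 lists one, its name blacked out, that "equals the sum of the MCS-SF, MCS-RB and PGA subscores".

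**Windows.** The footnote to SAP Table 3 says that "time windows will be applied excluding assessments performed more than 2 days after the last dose of IP". It makes an exception for endoscopy and one blacked-out item, "where assessments performed more than 7 days after last dose will be excluded", and extends their Week 6 window to Day 52. SAP Table 4 applies the 2-day limit to diary data.

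**The concern.** The two kinds of partial Week 6 data seem to be treated unequally. If endoscopy is missing and the other three subscores are present, the Week 6 blacked-out score is in the imputation model and informs the missing total. If endoscopy is present and SF, RB or PGA is missing, SF+RB+PGA cannot be formed either. The total is then imputed from earlier visits alone. A centrally read subscore worth up to 3 of the 12 points enters neither the total nor the imputation. The imputed total can even contradict it: given MCS-ES, the true total must lie between ES and ES + 9, and nothing holds the imputed value there.

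The comparison has 20 against 10 subjects, so precision on the primary endpoint is scarce, and the unused value comes from an invasive procedure already performed.

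**Working it through.** **1. Can the case arise?** Take a last dose on Day 35 and an ED visit with endoscopy on Day 40.
- MCS-ES: 5 days after last dose, inside the 7-day limit and the Day 37-52 window, so it is accepted.
- PGA on Day 40: 5 days after last dose, outside the 2-day limit, so it is excluded.
- Diary: within the Table 4 Week 6 window (Days 36-42), only Days 36 and 37 pass the 2-day limit. SAP 6.2.2 asks for 3 consecutive available days.

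The total is missing although MCS-ES is valid. This route is narrow. The earliest accepted Week 6 endoscopy is Day 37, so the last dose must fall on Day 37 - 7 = Day 30 or later. A missed PGA or a poorly kept diary is a second route.

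**2. Reference precision.** Inputs from SAP 2.6 and 6.2.2.3: 20 v 10, SD 3.3, TV -3.0, LRV -1.3, P10 and P80 rules. SE = 3.3 x sqrt(1/20 + 1/10) = 1.278. With a flat prior, a signal needs d + 0.8416 x SE < -1.3, and no signal means d - 1.2816 x SE >= -3.0.

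| True difference | | Signal | No conclusion | No signal |
|---|---|---|---|---|
| -3.0 | SAP | 0.673 | 0.220 | 0.107 |
| -3.0 | computed | 0.687 | 0.213 | 0.100 |
| -1.3 | SAP | 0.205 | 0.289 | 0.506 |
| -1.3 | computed | 0.200 | 0.281 | 0.519 |

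All six agree within 2 points.

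**3. Approximate cost by formula.** Let a fraction f be affected, and let R2 be the share of variance in the missing total that the imputation explains. Variance inflation is 1 + f/(1 - f) x (1 - R2). Both f and R2 are assumptions.
- f = 0.10, R2 from 0.5 to 0.8 once MCS-ES is used: 1.278 x sqrt(1.0556) = 1.313 against 1.278 x sqrt(1.0222) = 1.292. The SE is 1.6% smaller.
- f = 0.20, same R2: 1.278 x sqrt(1.125) = 1.356 against 1.278 x sqrt(1.05) = 1.310. The SE is 3.4% smaller. The 90% CI half-width goes from 2.23 to 2.15, and the signal probability at -3.0 from 0.660 to 0.676.

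Over R2 of 0.3-0.6 without MCS-ES and 0.45-0.8 with it, the reduction is 0.3-0.8% at f = 0.05, 0.5-1.6% at 0.10 and 1.1-3.4% at 0.20.

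**4. Simulation of the small arms.** There were 1,500 trials per setting, with Gaussian subscores, Bayesian regression imputation (40 imputations), ANCOVA on baseline MCS and three assumed correlation settings. Entries are the empirical SE, first with the SAP's variables (taking the blacked-out score as SF+RB+PGA), then with SF+RB+PGA imputed and the measured MCS-ES added.

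| Affected | By arm | SE reduction | Pooled | SE reduction |
|---|---|---|---|---|
| 5% | 1.089 to 1.074; 1.169 to 1.157; 1.087 to 1.075 | 1.0-1.4% | 1.107 to 1.100; 1.162 to 1.152; 1.044 to 1.032 | 0.6-1.1% |
| 10% | 1.184 to 1.136; 1.232 to 1.198; 1.095 to 1.058 | 2.8-4.1% | 1.121 to 1.098; 1.173 to 1.156; 1.101 to 1.079 | 1.4-2.1% |
| 20% | 1.337 to 1.275; 1.380 to 1.295; 1.235 to 1.146 | 4.6-7.2% | 1.146 to 1.111; 1.253 to 1.209; 1.094 to 1.044 | 3.1-4.6% |

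A further simulation, with the model size unchanged and correlations of 0.5-0.7, gave 3-5% by arm and 1-2% pooled with 3 of 30 affected. With 6 of 30 it gave 7-10% and 3-5%.

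**5. Why MCS-ES cannot simply be added.** If the blacked-out score is SF+RB+PGA, then at Week 6 total - (SF+RB+PGA) - ES = 0 for every complete subject. A multivariate normal model holding all three has an exactly singular covariance matrix. The pooled fallback holds the same three variables and is singular too, so the SAP's sequence would end at the model without treatment. Using MCS-ES as one more regression predictor by arm is also unsafe: six coefficients would be fitted in a placebo arm of 10 less the affected subjects. In the simulation the by-arm SE rose in 8 of 9 settings, for example from 1.232 to 1.491.

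**The case against.** **The variable is blacked out.** The list in SAP 6.2.2.2 is partly redacted, and the Appendix VIII code that would settle it is not in the text available. This stands. A reader might infer that the SAP certainly leaves out MCS-ES. The visit timing makes that a strong inference but does not prove it. The second item in the 7-day exception is also blacked out. I take it not to be PGA, because PGA is named openly elsewhere.

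**The rule is coherent.** Setting a composite to missing and multiply imputing it from longitudinal scores is a legitimate pre-specified choice, and Sensitivity Analysis 2 gives an observed-case result. This stands as far as bias goes. A reader might infer that the treatment estimate is biased, but nothing in the documents shows it. Sensitivity Analysis 2 does not recover the unused value, because it drops these subjects.

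**Few subjects may be affected.** PGA and endoscopy belong to the same visit, the diary is daily, and many dropouts will lack endoscopy as well. This stands, and it limits the size.

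**Part of the by-arm loss has another cause.** In the simulation, observed-case ANCOVA had a smaller SE than the planned by-arm imputation in 8 of 9 settings (for example 1.136 against 1.184 at 10%). Fitting the imputation in 10 placebo subjects is itself costly. The fix brings the by-arm SE to about the observed-case level.

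**The decision rule may not be touched.** A reader might infer that the P10/P80 decision is degraded. SAP 6.2.2.3 leaves its details to a separate document and does not say that the imputed estimate feeds it.

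**Conclusion.** The point holds conditionally. If the blacked-out score is SF+RB+PGA, a subject with a valid Week 6 MCS-ES but a missing SF, RB or PGA is imputed without the measured MCS-ES. The unequal windows for endoscopy and the other components make such subjects possible.

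The consequence is some lost precision. Using MCS-ES makes the SE about 1-5% smaller with 3 of 30 affected and 3-10% smaller with 6 of 30, under assumed correlations of 0.5-0.7. The formula in the working gives the lower figures and the by-arm simulations the higher ones. The affected rate is an assumption throughout. At 5% affected the gain is about 1% or less by most of these calculations. The change is worth making because it costs little, not because the primary analysis is unsound.

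**What to change.** First confirm from the Appendix VIII code which variables are in the imputation model. If Week 6 MCS-ES is absent, amend SAP 6.2.2.2 as follows:

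1. Do not impute the total. Replace Week 6 total MCS in the model by Week 6 SF+RB+PGA and Week 6 MCS-ES.
2. Drop the baseline blacked-out score, which is largely contained in baseline MCS. The variables are then baseline MCS, SF+RB+PGA at Weeks 2, 4 and 6, and Week 6 MCS-ES: five in place of six. An affected subject is still imputed from four predictors.
3. Impute only the part that is missing, and form the total as observed plus imputed parts in each imputed dataset.
4. Leave the ANCOVA, Rubin pooling and singularity fallbacks unchanged.
5. Do not keep Week 6 total MCS in the model beside its two parts.

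SAP 6.2.2.1 should say that the missing-total rule governs the observed-case derivation and does not discard observed parts at imputation. SAP 4.3.3 should say whether the different 2-day and 7-day limits within one composite are intended.

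The cost is a short SAP edit, a changed variable list and one derivation step after imputation; no new data are needed. The small downside is that a discrete 0-3 score is treated as normal in the imputation model.
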